**10.8. Appendix 8: Study Conduct During a Natural Disaster****GUIDANCE ON STUDY CONDUCT DURING THE COVID-19 PANDEMIC**

It is recognized that the CORONAVIRUS DISEASE 2019 (COVID-19) may have an impact on the conduct of this clinical study due to, for example, isolation or quarantine of participants and study site personnel; travel restrictions/limited access to public places, including hospitals; study site personnel being unavailable, isolated, or reassigned to critical tasks.

The sponsor is providing options for study-related participant management in the event of disruption to the conduct of the study. This guidance does not supersede any local or government requirements or the clinical judgement of the investigator to protect the health and well-being of participants and site staff. If, at any time, a participant's travel to the study site is considered to be dangerous, study participation may be interrupted, and study follow-up conducted. If it becomes necessary to discontinue participation in the study, the procedures outlined in the protocol for discontinuing study intervention will be followed.

If, as a result of the COVID-19 pandemic scheduled visits cannot be conducted in person at the study site, they will be performed to the extent possible remotely/virtually or delayed until such time that on-site visits can be resumed. At each contact, participants will be interviewed to collect safety data. Key immunogenicity endpoint assessments should be performed if required and as feasible. Participants will also be questioned regarding general health status to fulfill any physical examination requirement.

Every effort should be made to adhere to protocol-specified assessments for participants on study intervention, including follow-up. Modifications to protocol-required assessments may be permitted after consultation with the participant, investigator, and the sponsor. Missed assessments/visits will be captured in the clinical trial management system for protocol deviations. Discontinuations of study interventions and withdrawal from the study should be documented with the prefix "COVID-19-related" in the

If the participant has tested positive for COVID-19, the investigator should contact the sponsor's responsible medical officer to discuss plans for administration of study intervention, performing study assessments, and follow-up. Modifications made to the study conduct as a result of the COVID-19 pandemic should be summarized in the Clinical Study Report.

---

**GUIDANCE SPECIFIC TO THIS PROTOCOL:****Screening and Randomization**

- Enrollment of new participants may continue based on the investigator's assessment of risks versus benefits, depending on the situation at a particular site, and the ability to monitor participant safety.

**Site Visits**

- When site visits are not possible due to local/national guidelines, sites should collect the assessments via telephone visits or home-based visits, if the participant allows. The actual visit date and the type of visit (ie, telephone or home-based visit) should be captured in the eCRF according to the eCRF completion guidelines. Procedures that cannot be performed during a home-based visit (eg, blood samples), should be excluded.

**Vaccine Administration**

- When planning for vaccination visits, local/national or institutional guidelines will be followed. The study vaccine must be administered by a blinded qualified individual at the study site. If this is not possible, a solution may be considered in consultation with the sponsor and taking into consideration participant safety.

**Informed Consent Form**

- Consenting and re-consenting of participants for the measures taken (including also remote consenting by phone or video consultation) will be performed as applicable and according to local guidance for informed consent applicable during the COVID-19 pandemic. The process is to be documented in the source documents.

**Source Data Verification/Monitoring**

- In case on-site monitoring visits are not possible, the site monitor may contact the investigator to arrange monitoring visits and activities remotely (in accordance with site and local requirements). Additional on-site monitoring visits may be needed in the future to catch up on source data verification.

**Site Audits**

- During the COVID-19 pandemic and at the impacted sites, study site GCP audits with direct impact/engagement from the investigator and study site personnel would not be conducted in order to comply with national, local, and/or organizational social distancing restrictions. Additional quality assurance activities such as remote audits or focused review of study-related documents may take place with limited impact/engagement if possible.

## **10.9. Appendix 9: Protocol Amendment History**

This is an original protocol.

**VERSION HISTORY****Table 1 – SAP Version History Summary**

SAP Version	Approval Date	Change	Rationale
1.0	23-Jun-2022	Not Applicable	Initial release

## 1. INTRODUCTION

This statistical analysis plan (SAP) contains information needed to perform the complete safety and immunogenicity analysis of the VAC18195RSV1001 trial. It applies to all the analyses described in Section 9.4 of the clinical trial protocol (CTP). The specifications of individual tables, listings, and figures to be generated in each analysis will be described in a separate data presentation specifications (DPS) document.

### 1.1. Objectives and Endpoint

Refer to Section 3 of the CTP.

### 1.2. Study Design

Please refer to Section 4.1 of the CTP for more details on the study design, and Section 6.3 of the CTP for details on randomization and procedures for maintaining the blind.

## 2. STATISTICAL HYPOTHESES

No formal hypothesis will be tested. All the statistical analyses will be performed descriptively.

## 3. SAMPLE SIZE DETERMINATION

Refer to Section 9.2 of the CTP.

## 4. POPULATIONS (ANALYSIS SETS) FOR ANALYSIS

For vaccine studies, study intervention assignment will follow the as-treated principle. The analysis sets are defined in the [Table 2](#).

**Table 2 – Analysis sets**

Analysis Sets	Description
All screened	This analysis set includes all participants screened for the study, regardless of whether they were screen failures or they got enrolled in the study. Rescreened participants are counted only once.
Randomized	The randomized analysis set includes all participants who were randomized in the study.
Full Analysis Set (FAS)	The full analysis set (FAS) will include all participants who received the study vaccine, regardless of the occurrence of protocol deviations. All safety and participant information analyses will be based on the FAS.
Per-protocol Immunogenicity (PPI) Set	The Per-protocol Immunogenicity (PPI) Set will include all randomized participants who received the planned study vaccine(s) and for whom immunogenicity data are available. Samples taken after a participant experiences a major protocol deviation expected to impact the immunogenicity outcomes will be excluded from the PPI analysis. The list of major protocol deviations that would lead to elimination from the immunogenicity analysis will be specified in the major protocol deviation criteria

Analysis Sets	Description
	document, which will be finalized before database lock and unblinding. The analysis of all immunogenicity endpoints will be based on the PPI Set. For key tables, sensitivity immunogenicity analyses might also be performed on the FAS.

## 5. STATISTICAL ANALYSES

### 5.1. General Considerations

#### 5.1.1. Study phases

A baseline (or reference) value will be defined as the value of the last available assessment prior to vaccination on Day 1. If there was no immunogenicity assessment done pre-vaccination, the earliest assessment post-vaccination on Day 1 (but not exceeding Day 1) can be used as the baseline value for the immunogenicity analysis, if available.

The results of the safety analysis will be presented by phase. Immunogenicity results will be presented per scheduled time point as appropriate. Listings will be shown per phase and time point.

Study day or relative day is defined as follows:

- Study Day = visit date – date of Day 1 + 1; if visit date  $\geq$  date of Day 1 (date of vaccination).
- Study Day = visit date – date of Day 1; if visit date  $<$  date of Day 1 (date of vaccination).

#### 5.1.2. Phase definition

The phases in the study will be constructed as follows:

**Table 3 – Phase definitions**

Phase	Phase #	Period	Period #	Interval	
				From	To
Screening	1			Date and time of signing	One minute prior to start of the Post-dose period
Regimen	2	Post-dose 1	1	Date and time of the first vaccination	Minimum of: a) 23:59 at the date of last contact (for early discontinuation) b) 23:59 at the database cut-off date for analyses conducted before the final analysis c) maximum of (28 days after vaccination at 23:59, scheduled visit 28 days after vaccination at 23:59)

Follow-up 1	3			One minute after Post-dose 1 period end	Minimum of: a) 23:59 at the date of last contact (for early discontinuation or participants that completed the study) b) 23:59 at the database cut-off date for analyses conducted before the final analysis c) End of Study Visit day at 23:59 d) date/time of second vaccination
Regimen	2	Post-dose 2	2	Date and time of the second vaccination	Minimum of: a) 23:59 at the date of last contact (for early discontinuation) b) 23:59 at the database cut-off date for analyses conducted before the final analysis c) maximum of (28 days after vaccination at 23:59, scheduled visit 28 days after vaccination at 23:59)
Follow-up 2	4			One minute after Post-dose 2 period end	Minimum of: a) 23:59 at the date of last contact (for early discontinuation or participants that completed the study) b) 23:59 at the database cut-off date for analyses conducted before the final analysis c) maximum of (End of Study Visit, scheduled visit 182 days after vaccination at 23:59)

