**Table 9: Visit Windows: Cohort 1 and 2**

| Clinic Visit # | Visit Day | Visit Window | Primary Purpose                                                  |
|----------------|-----------|--------------|------------------------------------------------------------------|
| 3              | 8         | + 3 days     | 7 days post study vaccination, Safety visit                      |
| 4              | 15        | + 3 days     | 14 days post study vaccination, Immunogenicity and Safety visit  |
| 5              | 29        | + 7 days     | 28 days post study vaccination, Immunogenicity and Safety visit  |
| 6              | 85        | + 7 days     | 3 months post study vaccination, Immunogenicity and Safety visit |
| 7              | 183       | ± 14 days    | 6 months post study vaccination, Immunogenicity and Safety visit |
| 8              | 365       | ± 1 month    | 1 year post study vaccination, Immunogenicity visit              |
| 9              | 730       | ± 1 month    | 2 years post study vaccination, Immunogenicity visit             |
| 10             | 1095      | ± 1 month    | 3 years post study vaccination, Immunogenicity visit             |

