### 5.3. Primary Endpoint(s) Analysis

#### 5.3.1. Definition of Endpoints

For cohort 1 to 3 the primary safety endpoints are defined as:

- Serious adverse events (SAEs) and adverse events of special interest (AESIs) from first dose administration until 6 months after vaccination
- Solicited local and systemic adverse events (AEs) for 7 days after vaccine administration
- Unsolicited AEs from the time of vaccine administration through the following 28 days

In addition, for cohorts 1 and 2, and cohort 4 the primary immunogenicity endpoint is defined as RSV neutralization antibody titers.

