#### 5.3.2. Analysis Methods for the Primary Safety endpoints

No formal statistical testing of safety data is planned. Safety data will be analyzed descriptively by cohort (or pooled over cohorts, as applicable) and study arm, and by group (cohort 1), as applicable, per phase and across the entire study period. All safety analyses will be made on the FAS.

The verbatim terms used in the eCRF by investigators to identify AEs will be coded using the Medical Dictionary for Regulatory Activities (MedDRA). Any AE occurring at or after the first vaccination is considered to be treatment emergent. All reported AEs with onset during the active phase (ie, AEs occurring after vaccination up to 28 days post-vaccination) or AEs present before the active phase but worsening during the active phase, and all SAEs, AEs leading to study or vaccine discontinuation during the study, potential AESIs and AESIs (up to 6 months after vaccination) will be included in the analysis. For each AE, the percentage of participants who experience at least 1 occurrence of the given event will be summarized. All other unsolicited adverse events collected outside the 28-day period will be presented through listings.

AESIs (as determined in Section 5.3.2.1) will be reported until 6 months post vaccination and additionally by different time periods:

- 0 – 28 days post dose,
- 29 days – 56 days post dose,
- 0 – 56 days post dose,
- 57 days – 6 months post dose,
- 0 – 6 months post-dose.

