**Definition of intervals:**

Dose	Interval	From	to
Post-vaccination 1	0-28 days post dose	Date time of the 1 st vaccination	Min of: 
 
23:59 at the date of last contact (for discontinuations)
 
23:59 at date of DB cut-off for interim analyses
 
Maximum(Date of Vaccination 1 + 28 days at 23:59, date of scheduled visit 4 weeks after 1st vaccination at 23:59)
 

	29-56 days post dose	One minute after the end of the interval 0-28 days post dose	Min of: 
 
23:59 at date of last contact (for discontinuations)
 
23:59 at date of DB cut-off for interim analyses
 
Date of Vaccination 1 + 56 days at 23:59
 

	57 days - 6 months post-dose	One minute after the end of the interval 29-56 days post dose	Min of: 
 
23:59 at date of last contact (for discontinuations)
 
23:59 at date of DB cut-off for interim analyses
 
Maximum of (Date of Vaccination 1 + 183 days at 23:59, date of scheduled visit 183 days post 1st vaccination at 23:59)
 

	>6 months post-dose	One minute after the end of the interval 57 days - 6 months post-dose	Min of: 
 
23:59 at the date of last contact (for discontinuations)
 
23:59 at the date of DB cut-off for interim analyses
 

			
 
1 min prior to date time of vaccination 2
 

Post-vaccination 2	0-28 days post dose	Date time of the 2nd vaccination	Min of: 
 
23:59 at the date of last contact (for discontinuations)
 
23:59 at date of DB cut-off for interim analyses
 
Maximum(Date of Vaccination 2 + 28 days at 23:59, date of scheduled visit 4 weeks after 2nd vaccination at 23:59)
 

	29-56 days post dose	One minute after the end of the interval 0-28 days post dose	Min of: 
 
23:59 at date of last contact (for discontinuations)
 
23:59 at date of DB cut-off for interim analyses
 
Date of Vaccination 2 + 56 days at 23:59
 

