	57 days - 6 months post-dose	One minute after the end of the interval 29-56 days post dose	Min of: 
 
23:59 at date of last contact (for discontinuations)
 
23:59 at date of DB cut-off for interim analyses
 
Maximum (Date of Vaccination 2 + 183 days at 23:59, day 547 visit at 23:59)
 

	>6 months post-dose	One minute after the end of the interval 57 days - 6 months post-dose	Min of: 
 
23:59 at the date of last contact (for discontinuations)
 
23:59 at the date of DB cut-off for interim analyses
 

The combination of the '0 - 28 days post-dose' interval and the '29 - 56 days post-dose' interval will be referred as '0 - 56 days post-dose'.

The combination of the '0 - 28 days post-dose', '29 - 56 days post-dose' and '57 days - 6 months post-dose' intervals will be referred as '0-6 months post-dose'.

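### The SAP lets the AESI 0-28 day interval and the Post-dose period run to a late 4-week visit, so the 0-28 and 29-56 day AESI counts do not match their labels

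*SAP*

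**What the plan says.** SAP Table 3 closes Post-dose 1 and Post-dose 2 at the earliest of last contact, data cut-off and a third limb: "maximum of (28 days after vaccination at 23:59, scheduled visit 28 days after vaccination at 23:59". The *Definition of intervals* table in SAP 5.3.2.3 ends the AESI *0-28 days* interval by the same rule, "Maximum(Date of Vaccination 1 + 28 days at 23:59, date of scheduled visit 4 weeks after" the first vaccination, with a matching row for dose 2. The *29-56 days* interval begins "One minute after the end of the interval 0-28 days post dose" and ends at "Date of Vaccination 1 + 56 days at 23:59" (likewise for dose 2), so its start moves and its end does not.

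Elsewhere the SAP works with a plain 28 days. Section 5.3.1 defines the endpoint as "Unsolicited AEs from the time of vaccine administration through the following 28 days". Section 5.3.2 describes the active phase as lasting until 28 days after vaccination, sends other unsolicited AEs from outside that period to listings, and names "29 days – 56 days post dose" as an AESI reporting period.

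Protocol Table 9 places the "28 days post study vaccination, Immunogenicity and Safety visit" on Day 29 with a window of + 7 days, late only. Tables 10 and 11 give the same window for Cohorts 3 and 4 and for dose 2.

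For dose 2, the *57 days - 6 months* interval ends, apart from discontinuation and cut-off, at the later of vaccination 2 + 183 days and the "day 547 visit at 23:59". The dose-1 row uses the date of its own scheduled 6-month visit.

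**The concern.** The AESI in this study is thrombosis with thrombocytopenia syndrome. Protocol 2.2 says that symptoms after the sponsor's COVID-19 vaccine usually began within 1 to 4 weeks and sometimes later, so a boundary at 28 days bears directly on what these intervals are meant to show. If the boundary moves with the visit, an event 33 days after dosing is counted as 0-28 days in a participant seen on day 34, and as 29-56 days in one seen on day 28.

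The shift has one direction: a late visit lengthens the early interval, and an early or on-time visit leaves it unchanged. Potential AESIs cover thrombotic events and any platelet count below the laboratory's lower limit, and Protocol Appendix 7 includes myocardial infarction and stroke. Background events are therefore to be expected at age 60 and over. They are collected for 6 months (Protocol 8.3.1), so the extra days are fully observed. SAP 5.3.2.2 divides by participants in the population, phase and arm, not by person-time, so nothing corrects for unequal lengths.

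There is also a contradiction for the programmer. Take an unsolicited AE that starts 32 days after vaccination in a participant seen on day 33. Table 3 with Step 1 of SAP 5.3.2.3 places it in Post-dose. SAP 5.3.2 places it outside the active phase and in a listing.

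**Working it through.** Count days from vaccination, with the vaccination day as 0. The SAP's Study Day is this count plus 1.

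**Inputs**
- Visit at v days after vaccination. In-window range 28 to 35, which is Study Day 29 to 36 (Protocol Tables 9 to 11). The SAP Table 4 upper limit for Day 29 is also Study Day 36.
- End of the early interval: E = max(28, v) (SAP Table 3 and 5.3.2.3).
- End of *29-56 days*: fixed at 56 (SAP 5.3.2.3).

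**Formulas**
- Length of *0-28 days* = E + 1.
- Length of *29-56 days* = 56 - E.

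The labels are reproduced only when the visit is on or before day 28: 28 + 1 = 29 and 56 - 28 = 28.

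| Visit (days after vaccination) | 0-28 days | 29-56 days | Sum |
|---|---|---|---|
| 28 | 29 | 28 | 57 |
| 31.5 (assumed mean delay 3.5 days) | 32.5 (+12%) | 24.5 (-12.5%) | 57 |
| 35 (window limit) | 36 (+24%) | 21 (-25%) | 57 |
| 42 (out of window) | 43 (+48%) | 14 (-50%) | 57 |

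The 3.5-day row is the mean if lateness is spread evenly over 0 to 7 days. That is an assumption. With a flat background rate, the ratio of early to later events would be 29/28 = 1.04 as labelled, 32.5/24.5 = 1.33 with the assumed mean delay, and 36/21 = 1.71 if every visit fell on the last permitted day.

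The sum stays at 57 days for any visit up to day 56, so *0-56 days* does not move. After day 56 the *29-56 days* interval would end before it starts.

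**The other reading of the rule.** If *scheduled visit* meant the nominal date, both arguments of the maximum would be vaccination + 28 days and the rule would do nothing. The actual visit date is the only reading with an effect.

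**Size in events (illustration).** Assume a constant rate of 0.5% per 29 days and take the largest pooled group in Protocol Table 17, N = 600. Expected early events as labelled: 600 x 0.005 = 3.0. Later events: 3.0 x 28/29 = 2.9.
- Mean delay 3.5 days: 3.0 x 32.5/29 = 3.4 early and 3.0 x 24.5/29 = 2.5 later.
- All at the window limit: 3.0 x 36/29 = 3.7 early and 3.0 x 21/29 = 2.2 later.

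**Day 547.** 365 + 182 = 547, so the name fits the Schedule of Activities (visit 13 at X + 182) only if Day X is Day 365. The protocol leaves Day X open, at 12 months or later. With the ± 14 day window, visit 13 can fall at 182 + 14 = 196 days after dose 2. Where the named visit does not exist, the interval closes at day 183, leaving up to 196 - 183 = 13 days before a late in-window visit in the *>6 months* row. Protocol Table 11 gives X + 183 for this visit, so the figure is approximate.

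**The case against.** The best defence is that little of importance depends on this boundary. The SAP is descriptive, plans no early-versus-late ratio and reports incidence by arm. The intervals are unequal by design in any case: *57 days - 6 months* is about 183 - 56 = 127 days long, so nobody should compare raw counts across all of them. *0-56 days* and *0-6 months* are also reported and do not move with the 4-week visit unless it falls after day 56. A visit-based end also keeps events found at that visit in the active period, which is a defensible convention. All of this stands, and it limits the harm. It does not make a count labelled 0-28 days correct when it covers up to 36 days or more, nor does it reconcile Table 3 with SAP 5.3.2.

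Four stronger readings are tempting, and the documents do not support them.
- *The 28-day primary safety counts are wrong.* Solicited AEs are recorded for 7 days and are unaffected. Other unsolicited AEs are collected only to 28 days (Protocol 8.3.1), so few can enter late. SAEs and AESIs have a 6-month endpoint; no 28-day SAE endpoint exists.
- *Vaccine is biased against placebo.* Arms are randomized and blinded on one visit schedule, so lateness should be similar across them.
- *A false early excess of 1.71 is to be expected.* That figure requires every participant to attend on the last permitted day. The event shifts shown above are well under one event in 600 participants and could not be told from chance.
- *Events around day 547 are lost.* The maximum always covers 183 days, subject to discontinuation and cut-off, and later events move to *>6 months*. They are reclassified.

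**Conclusion.** The point holds as a mismatch between definitions and labels that affects within-arm AESI timing, and SAE tabulation by phase in the same way. The early interval is 29 days as labelled and up to 36 days with an in-window visit; the next falls from 28 to 21 days. Under the assumed mean delay of 3.5 days they are 32.5 and 24.5 days. The size in practice depends on actual visit lateness, which the documents do not give, and on how many visits fall outside the window, where the rule has no cap.

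The conflict between Table 3 and SAP 5.3.2 needs no assumption: for an event after day 28 and on or before a late visit, the two give different answers. The day 547 reference is a separate and smaller defect. It matters only if Day X is not Day 365, and then for at most about 13 days of dose-2 follow-up, which would fall outside the reported *0-6 months* period.

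**What to change.** 1. In the SAP 5.3.2.3 interval table, for both doses, end *0-28 days* at vaccination + 28 days at 23:59 (keeping the last-contact and cut-off limbs) and start *29-56 days* one minute later. Every participant followed that long then has 29 and 28 days, whatever the visit date.
2. In SAP Table 3, end Post-dose 1 and Post-dose 2 at the same fixed point, so that they agree with the 28-day active phase in SAP 5.3.2.
3. In the dose-2 *57 days - 6 months* row, replace the day 547 visit with the date of the scheduled visit 6 months after the second vaccination, as the dose-1 row does.

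If a visit-based end is preferred, the intervals should be relabelled and person-days reported beside the counts. This cures the label but leaves the lengths unequal, so the fixed cut is simpler.

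The cost is a few SAP table edits and date programming. Data collection, visits and sample size do not change.
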